## Statistical methods planned in the protocol and determination of sample size

### Statistical and analytical plans

This document describes the statistical methodology for analyses of efficacy and safety in Study CZOL446H2337E1. The purpose of this study is to extend the period of observation in patients who have completed one year of evaluation in the Core study (CZOL446H2337) to evaluate the long-term safety and efficacy of zoledronic acid in osteoporotic children or adolescents treated with glucocorticoids. To ensure adequate intake of calcium and vitamin D, all children enrolled in this study will be provided with conservative intervention (diet with or without supplements), regardless of their treatment assignment.

The primary objective of this study is to demonstrate that zoledronic acid given long-term, over an additional 12 months from the Core study (CZOL446H2337), is safe for the treatment of osteoporotic children treated with glucocorticoids.

The secondary objectives include:

1. To evaluate the change from core baseline in LS-BMD Z-score at Month 18 and 24 by core treatment group.
2. To evaluate the change from core baseline in LS and total body BMC at Month 18 and 24 by core treatment group.
3. To evaluate the change from core baseline in serum N-terminal propeptide type I collagen (PINP), cross linked N-telopeptide (NTX), bone specific alkaline phosphatase (BSAP) and tartrate-resistant acid phosphatase isoform 5b (TRAP-5b) at Month 18 and 24 by core treatment group.
4. To evaluate the proportion of patients with new clinical vertebral fractures during the 12 month extension period by core treatment group.
5. To evaluate the proportion of patients with new morphometric vertebral fracture during the 12 month extension period by core treatment group.
6. To evaluate the change from core baseline in pain using the Faces Pain Scale-Revised (FPS-R) at Month 15, 18, 21 and 24 by core treatment group.
7. To evaluate the change from core baseline in 2nd metacarpal cortical width at month 24 by core treatment group.
8. To evaluate the change from core baseline in bone age and 2nd metacarpal cortical width at month 24 by core treatment group.

Categorical data will be presented as frequencies and percentages. For continuous data, mean, standard deviation, median, minimum, and maximum will be presented.

### General considerations

#### Baseline definition

Unless otherwise specified, the following general rules will be applied for defining baseline.

- Core baseline: core baseline is defined as the last non-missing measurement on or prior to the date of first study drug infusion in core study.

- Extension baseline: extension baseline is defined as the last non-missing measurement on or prior to the date of first study drug infusion in the extension study. If no extension assessments are available on or prior to the first drug infusion in the extension study, the last assessment in core study will be used instead.

## **Study day**

The general rules for calculating the study day are as follows:

Core Study Day:

- If the event date occurs before the first infusion date in core study, then the core study day is defined as the date of the event minus the first infusion date in core study;
- If the event date occurs after the first infusion date (inclusive) in core study, then the core study day is defined as the date of the event minus the first infusion date in core study plus 1.

Extension Study Day:

- If the event date occurs before the first infusion date in the extension study, then the extension study day is defined as the date of the event minus the first infusion date in the extension study;
- If the event date occurs after the first infusion date (inclusive) in the extension study, then the extension study day is defined as the date of the event minus the first infusion date in the extension study plus 1.

## **Visit schedule**

Summaries by visit will be based on the visits collected on the CRF and no visit window will be applied. Only scheduled visits will be included in the summary, unless specified otherwise.

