5.6.2 Discontinuation of study treatment

Discontinuation of study treatment for a patient occurs when study drug is stopped earlier than the protocol planned duration i.e. before Visit 12, Month 18, and can be initiated by either the patient, parent/legal guardian or the investigator.

The investigator must discontinue study treatment for a given patient if he/she believes that continuation would negatively impact the risk/benefit of trial participation.

Study treatment must be discontinued under the following circumstances:

- Patient or parent/legal guardian's wish
- Pregnancy (see [Section 6.5.5](#) and [Section 7.4](#))
- Use of prohibited treatment as per recommendations in [Section 5.5.8](#)
- Any situation in which study participation might result in a safety risk to the patient
- Emergence of the following adverse events:

- ONJ
- Renal failure
- Any laboratory abnormalities that in the judgment of the investigator, taking into consideration the subject's overall status, prevents the subject from continuing participation in the study

If discontinuation of study treatment occurs, the patient should NOT be considered withdrawn from the study. The patient should return to the clinic as soon as possible, after discontinuation of study drug, for a study treatment discontinuation (TD) visit. Treatment discontinuation visit assessments detailed in Visit 15 (Month 24) in [Table 6-1](#) or [Table 6-2](#) should be completed and recorded in the CRF. The investigator must determine the primary reason for the patient's premature discontinuation of study treatment and record this information on the Dosage administration record CRF and the study completion CRF.

After study treatment discontinuation, at a minimum, in abbreviated visits, the following data should be collected at clinic visits or via telephone visits:

- new / concomitant treatments
- adverse events (AEs)/serious adverse events (SAEs)

If the patient, parent/legal guardian cannot or is unwilling to attend any visit(s), the site staff should maintain regular telephone contact with the patient and parent/legal guardian, or with a person pre-designated by the patient or parent/legal guardian. This telephone contact should preferably be done according to the study visit schedule and changes recorded in the relevant pages of the CRF.

[figure not shown]

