5.6.5 Early study termination by the sponsor

The study can be terminated by Novartis at any time for any reason. This may include reasons related to the benefit risk assessment of participating in the study, practical reasons, or for regulatory or medical reasons (including slow enrolment). Should this be necessary, the patient must be seen as soon as possible and treated as a prematurely withdrawn patient. The investigator may be informed of additional procedures to be followed in order to ensure that adequate consideration is given to the protection of the patient's interests. The investigator will be responsible for informing the Institutional Review Board/Independent Ethics Committee (IRBs/IECs) of the early termination of the trial.

6 Visit schedule and assessments

[Table 6-1](#) and [Table 6-2](#) list all of the assessments and indicate with an "X" when the visits are performed.

Patients must be seen for all visits on the designated day, or as close to it as possible. Missed or rescheduled visits should not lead to automatic discontinuation. Patients who prematurely discontinue the study for any reason should be scheduled for a visit as soon as possible, at which time all of the assessments listed for the final visit will be performed. At this final visit, all dispensed investigational product should be reconciled and the adverse event and concomitant medications reconciled on the CRF.

Patients will be contacted for safety evaluations during the 30 days following the last administration of study treatment.

Table 6-1 Group 1 Assessment schedule

	Final visit of Core study		Infusion visit		Tele-phone	Infusion visit		Tele-phone		Notes
Visit	8	8A	9	10	11	12	13	14	15/EOS and TD and/or PSW	Visit 8 is the Core study completion visit. Visit 8A lists the additional assessments which need to be completed for the Extension study. Visits 8 and 8A assessments must be completed on the same day. Visits 8, 8A, and 9 can occur on the same day
Months relative to the Core study (after Visit 9 - Baseline of Extension study)			up to 10 months after V5 (Core study)	10 days after V9	15 (3 months after V9)	18 (6 months after V9)	10 days after V12	21 (9 months after V9)	24 (12 months after V9)	
Obtain informed consent (D) and assent (S)		X								
Inclusion/exclusion criteria (S)		X	X							
Prior/concomitant medications including GCs (D)	X	X	X	X	X	X	X	X	X	

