## Analysis for efficacy variables

If otherwise not specified, the efficacy data will be summarized and analyzed with respect to core baseline only and will be presented by the core treatment group and visit. The mean, median, standard deviations, and range of each variable and its change from baseline measured on a continuous scale, will be presented by core treatment group and visit. Number and percentage of patients will be presented for categorical variables by core treatment group and visit. All hypothesis tests will be evaluated at a 0.05 level of significance, and the p-values will be rounded to the 4th decimal place. Change from baseline at Month X is defined as value at Month X - value at baseline. Percentage change from baseline is defined as 100 times the change from baseline divided by the baseline value. Missing values will not be imputed or replaced.

The efficacy variables and their analysis methods are described below.

- **Percent change in lumbar spine areal BMD Z-score at Months 18 and 24 relative to baseline, zoledronic acid group vs. placebo**

The percent change in LS-BMD Z-score at Months 18 and 24 relative to core baseline between zoledronic acid and placebo (the core treatment groups) will be evaluated using an ANCOVA model with core treatment, pooled center, underlying condition treated with glucocorticoids and core baseline LS-BMD Z-score as explanatory variables and pooled centers as random effect.

From the model, core treatment difference in least squares means between zoledronic acid group vs. placebo group will be estimated and presented together with two-sided 95% CI and p-value. In the same table, the LS means and standard errors for percent change from baseline in LS-BMD Z-score at Month 18 and Month 24 will be presented for each core treatment group. Descriptive statistics will also be shown for baseline, Month 18 and Month 24 visits.

- **Change in lumbar spine and total body BMC at Months 18 and 24 relative to baseline, zoledronic acid group vs. placebo**

The change in BMC at the lumbar spine and total body at Months 18 and 24 relative to core baseline between zoledronic acid and placebo will be evaluated using an ANCOVA model with core treatment, pooled center, underlying condition treated with glucocorticoids and core baseline BMC as explanatory variables and pooled centers as random effect.

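### Early treatment-discontinuation and withdrawal assessments could be analysed as Month 24 results, because they share the Visit 15 column and the SAP has no rule that separates them

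*SAP*

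**What the plan says.** **Where early assessments are recorded.** In Protocol Tables 6-1 and 6-2 the last column is headed "15/EOS and TD and/or PSW". One set of assessments (DXA, spine and hand X-ray, bone markers, pain, laboratory tests and others) therefore serves the Month 24 visit, the TD visit and the premature-withdrawal visit.

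**When they are done.** Protocol 5.6.2 defines discontinuation of study treatment as stopping early, "i.e. before Visit 12, Month 18". It then says: "The patient should return to the clinic as soon as possible, after discontinuation of study drug", and the Visit 15 assessments are to be completed there. Protocol Section 6 likewise asks for the final-visit assessments, as soon as a visit can be arranged, from anyone who leaves the study early. After TD, the minimum later follow-up is new or concomitant treatments and adverse events.

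**How the SAP uses visits.** Under Visit schedule: "Summaries by visit will be based on the visits collected on the CRF and no visit window will be applied". The next sentence reads: "Only scheduled visits will be included in the summary, unless specified otherwise". Under Analysis for efficacy variables: "Missing values will not be imputed or replaced". The SAP defines an extension study day but does not use it to place TD or PSW records. It defines a new morphometric fracture by comparing the Month 24 X-ray with extension baseline.

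**The concern.** A TD visit held promptly after a stop before Month 18 falls about six months or more before Month 24. If that record carries the Visit 15 label, the SAP's CRF-visit rule places it in the Month 24 ANCOVAs, the Month 24 pain regression and the morphometric fracture count. Three things would follow:

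- The Month 24 means would mix 24-month values with much earlier ones.
- A fracture-free film at, say, 3 months would count as a negative result in a 12-month incidence.
- An early value would stand in for a missing Month 24 value, although the SAP rules out imputation or replacement.

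These comparisons are made between core arms with p-values. Unequal discontinuation is plausible, though not shown: core-placebo patients receive their first zoledronic acid at Visit 9, and Protocol 5.5.7.1 says post-dose symptoms typically come with the first infusion.

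**Working it through.** The plan gives no figure to reproduce. It states no discontinuation rate, and the sample size of about 100 is not a power calculation. The check is a reading of the text, followed by an illustration on assumed inputs.

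**Step 1: is a TD/PSW record a Month 24 record?**

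- *Included:* TD/PSW has a place in the assessment schedule, and that place is the Visit 15 column. A programmer can fairly treat it as scheduled Visit 15 data.
- *Excluded:* the visit is triggered by stopping drug, not by the calendar. Under the SAP's scheduled-visits sentence a programmer can fairly leave it out.

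Neither document gives the CRF label or chooses between these readings, so two programmers could build different Month 24 data sets.

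**Step 2: which analyses depend on the label?**

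- *Dependent:* LS-BMD Z-score, BMC, bone markers, metacarpal cortical width, pain at Month 24 and morphometric fracture. By-visit laboratory and vital-sign summaries and the end-of-study Tanner table also use it.
- *Not dependent:* adverse-event counts, and the SAP's new vertebral fractures, which run from first extension infusion to end of study.

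**Step 3: size if early values are included.**

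Assumptions: a share *d* of patients has a value taken *t* months after Visit 9 that is labelled Visit 15; change is linear in time; Visit 9 is at Month 12.

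- Shortfall in mean change from extension baseline = d × (1 − t/12)
- Shortfall in mean change from core baseline = d × (1 − (12 + t)/24)

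For d = 10% and t = 3:

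- extension baseline: 0.10 × (1 − 3/12) = 7.5%
- core baseline: 0.10 × (1 − 15/24) = 3.75%
- mean time of the Month 24 values: 24 − 0.10 × 9 = 23.1 months

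| d | t (months) | Extension baseline | Core baseline |
|---|---|---|---|
| 5% | 6 | 2.5% | 1.25% |
| 10% | 3 | 7.5% | 3.75% |
| 10% | 6 | 5.0% | 2.5% |
| 20% | 3 | 15.0% | 7.5% |
| 20% | 1 | 18.3% | 9.2% |

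The core-baseline column applies to most endpoints, since the SAP analyses efficacy against core baseline unless it says otherwise. Cortical width and pain use both baselines, but pain is analysed as decreased or not, so these percentages do not apply to it. If Visit 9 is delayed by the allowed 4 months, the core-baseline figure for 10% at 3 months becomes 0.10 × 9/28 = 3.2%. If TD/PSW records are excluded, the shortfall from this source is zero and those patients are missing at Month 24.

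**Step 4: direction of the between-arm contrast.**

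Let E be the extension-year change in an arm. Each arm's Month 24 mean loses d × (1 − t/12) × E. The contrast (core zoledronic acid minus core placebo) therefore shifts by the placebo arm's loss minus the zoledronic acid arm's loss. Everyone receives zoledronic acid in the extension. With equal *d* and *t*, and both changes positive, the contrast is overstated if the core-placebo arm gains more in that year and understated if it gains less. Unequal rates can move it either way.

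**The case against.** The strongest reply is that the SAP already closes the gap: only scheduled visits are summarised, and a visit triggered by stopping drug is not a scheduled Month 24 visit. The CRF is also not among the documents, and a shared column shows what to assess, not how the record is stored. Both points stand as far as they go. A reader might infer that early values will certainly be analysed as Month 24; the documents do not support that. They do not establish exclusion either, because TD/PSW sits within the schedule tables.

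Second, the early record need not be the patient's only one. Protocol 5.6.2 says a patient who stops drug is not to be considered withdrawn, and the abbreviated follow-up is a minimum, so a true Visit 15 may follow. This stands, and it adds a question: no rule says which record counts when both exist.

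Third, a reader might infer that the treatment effect is diluted. The arithmetic covers within-arm change only; Step 4 shows that the contrast can move either way.

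Fourth, the primary objective is safety, adverse-event counts do not use the label, and efficacy is secondary and unpowered. That limits the weight of the point but does not remove it, since the efficacy comparisons are still to be reported with p-values and confidence intervals.

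**Conclusion.** The point holds as a gap with a plausible wrong outcome, and the SAP should be changed. The shared column, the prompt timing of the TD visit and the no-window rule are all stated in the documents. Together they allow values taken many months early to be analysed as Month 24, unless the scheduled-visits sentence is read to exclude them.

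If they are included, 10% stopping at 3 months lowers the within-arm mean change by about 3.75% from core baseline and 7.5% from extension baseline. Over 5% to 20% stopping at 1 to 6 months, the ranges are about 1.25% to 9.2% and 2.5% to 18.3%. All of this rests on assumed rates, assumed timing and linear change; bone markers in particular need not change linearly.

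The clearest single effect is on morphometric fracture. The spine X-ray is scheduled only at Visit 8 and in the shared Visit 15 column, so an early film may be a patient's only extension film after baseline.

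**What to change.** Replace the no-window rule for TD/PSW records with a short SAP paragraph:

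1. Flag TD/PSW records separately from Visit 15. Count continuous and pain values as Month 24 only if the extension study day falls in a pre-stated window around day 365, with a similar window for Month 18. Never assign a post-infusion value to a baseline visit. List the rest.
2. If a patient has both a TD record and a later Visit 15, use Visit 15 for Month 24.
3. For morphometric fracture, keep a new fracture seen on a TD film as an event. Do not count a patient whose only film is early and fracture-free as having 12 months of fracture-free follow-up. Report the denominator.
4. Give the as-collected analysis as a sensitivity analysis.

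Assigning every early record to the nearest scheduled visit would not be safe: with X-rays only at Visits 8 and 15, an early post-infusion film could be assigned to baseline.

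**Cost.** One paragraph, one flag and a derivation from a study day that the SAP already defines; no new data. Somewhat fewer values reach the Month 24 analyses, and because nothing is imputed those patients are simply missing there, so the number excluded should be reported by core arm.

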## **Subjects and treatments**

The following analysis sets will be defined:

- Full Analysis Set (FAS)
- Safety Analysis Set (SAF)

### **Full Analysis Set (FAS)**

FAS includes all patients who have completed the core study and have received at least one dose of study medication in the extension study.

Screen failure patients are not considered as enrolled and excluded from FAS. Patients will be analyzed according to the treatment they were assigned to at the core study randomization.

All efficacy analyses will be performed using FAS.

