8. To demonstrate that zoledronic acid is safe for the treatment of osteoporotic children (with symptomatic vertebral fracture) treated with GCs, through the monitoring of relevant clinical and laboratory safety parameters.

3 Investigational plan

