9.1 Analysis sets

The following analysis sets are described:

Group 1 (patients who were randomized into the Core protocol)

- Full Analysis Set-1 (FAS-1)
- Safety Analysis Set-1 (SAF-1)

Group 2 (patients who were not randomized into the Core protocol)

- Full Analysis Set-2 (FAS-2)
- Safety Analysis Set-2 (SAF-2)

Full Analysis Set-1(FAS-1)

FAS-1 includes all patients who have completed the Core study and have received at least one dose of study medication in the Extension study.

Screen failure patients are not considered as enrolled and excluded from FAS-1. Patients will be analyzed according to the treatment they were assigned to at the Core study randomization.

Full Analysis Set-2 (FAS-2)

FAS-2 includes all patients who are enrolled in this Extension study and were not eligible to be randomized to the Core study because of having symptomatic (significant back-pain) vertebral fracture. Patients will be analyzed according to the treatment received at the Extension study.

All efficacy analyses will be performed separately using FAS-1 and FAS-2.

Safety Analysis Set-1 (SAF-1)

SAF-1 includes all patients who have completed the Core study and have received at least one dose of study medication in the Extension study. Patients will be analyzed according to the treatment received during the Core study. Patients will be analyzed as receiving zoledronic acid in the Core study if they received at least one dose of zoledronic acid in the Core study.

Safety Analysis Set-2 (SAF-2)

SAF-2 includes all patients those were not eligible to be randomized to the core study because of having symptomatic (significant back- pain) vertebral fractures and receive at least one dose of study medication in the Extension study.

- All safety analyses will be performed separately using SAF-1 and SAF-2.

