### **Safety Analysis Set (SAF)**

SAF includes all patients who have completed the core study and have received at least one dose of study medication in the extension study. Patients will be analyzed according to the

treatment received during the core study. Patients will be analyzed as receiving zoledronic acid in core study if they received at least one dose of zoledronic acid in core study.

All safety analyses will be performed using SAF.

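### The SAP's only two analysis sets require Core study completion, so any Group 2 patient dosed in the extension would be left out of the efficacy and safety analyses the protocol plans for that group

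*SAP*

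**What the plan says.** Protocol 9.1 defines four analysis sets: FAS-1 and SAF-1 for patients randomised into the Core study, and FAS-2 and SAF-2 for those who were not. It asks for efficacy separately on FAS-1 and FAS-2, and on safety states "All safety analyses will be performed separately using SAF-1 and SAF-2". Sections 9 to 9.5 plan descriptive, single-arm summaries for Group 2 with no hypothesis test. Section 9.4.1, on the safety variables, leaves the details to the SAP.

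Protocol 2.2 lists eight secondary objectives for Group 2. The eighth is safety: "To demonstrate that zoledronic acid is safe for the treatment of osteoporotic children (with symptomatic vertebral fracture) treated with GCs".

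The SAP defines two sets. For efficacy: "FAS includes all patients who have completed the core study and have received at least one dose of study medication in the extension study", with "All efficacy analyses will be performed using FAS". For safety: "SAF includes all patients who have completed the core study and have received at least one dose of study medication in the extension study", with "All safety analyses will be performed using SAF". In the FAS, grouping is by Core arm: "Patients will be analyzed according to the treatment they were assigned to at the core study randomization". The eight secondary objectives in the SAP are the Group 1 list, and its sample-size section mentions Core completers only.

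**The concern.** The protocol commits to reporting two populations, and the SAP is written for one. Group 2 is defined by not having been randomised into the Core study, so the SAP's membership rule shuts that group out. This goes further than missing detail. A programmer following the SAP to the letter would have to leave any dosed Group 2 child out of every adverse event, laboratory and vital-sign table.

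At stake are the eight Group 2 objectives, including safety in children with symptomatic vertebral fracture, and the agreement between the two documents on what will be reported. Where the SAP narrows the protocol's scope, the reader should find a reason, and the SAP text available gives none.

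**Working it through.** The documents give no figure to reproduce. The target of about 100 patients in protocol 9.6 has no power basis and is not split by group. The check is one of set membership and counting.

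**Step 1: who can enter each set.**

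| Set | Source | Core study condition | Extension dose required | Open to Group 2? |
|---|---|---|---|---|
| FAS-1, SAF-1 | Protocol 9.1 | completed | yes | no |
| FAS-2 | Protocol 9.1 | not eligible for randomisation | not stated | yes |
| SAF-2 | Protocol 9.1 | not eligible for randomisation | yes | yes |
| FAS, SAF | SAP | completed | yes | no |

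The two SAP sets correspond to FAS-1 and SAF-1. Of the protocol's 4 sets, 4 − 2 = 2 have no counterpart, and these are the two Group 2 sets. The number of Group 2 patients who can satisfy the SAP rule is 0, whatever the size of Group 2.

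**Step 2: which analyses use those sets.** The SAP ties all efficacy analyses to FAS and all safety analyses to SAF. The outputs not clearly tied to either are the recruitment count by country and center and the screen-failure listing, both under patient disposition. Neither answers a Group 2 objective.

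**Step 3: objectives matched to analyses.** Group 2 has 7 efficacy objectives + 1 safety objective = 8. The SAP text available provides an analysis for 0 of 8.

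**Step 4: is the restriction confined to the set definitions?** It is not.
- Results are laid out by Core treatment group, which Group 2 patients lack.
- Efficacy is measured by default from the Core baseline, which they also lack.
- The SAP's age bands cover 6 to 19 years, the Group 1 range. Group 2 admits ages 5 to 17.
- Group 2 is not named anywhere in the SAP text available.

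**Step 5: how many patients are affected.** The protocol's Amendment 3 status statement gives 12 enrolled at 10 May 2016, all in Group 1, so Group 2 stood at 12 − 12 = 0. Group 2 recruitment stayed open until Core randomisation finished (protocol 9.6). No later count is given.

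**The case against.** The best defence is that Group 2 may be empty. Amendment 2, which introduced it, is dated 15 January 2014, and nearly 28 months later nobody had been enrolled in it. The SAP also looks deliberately scoped. It contains GGT, total bilirubin and the Schwartz formula, which the amendment summary attributes to Amendment 3, so it was probably written against a protocol that already included Group 2. Its age bands and sample-size text fit Group 1 alone. This is consistent with an empty Group 2, or with Group 2 being reported elsewhere, but it establishes neither. Amendment 3 kept Group 2 open and revised its exclusion criteria. If the scoping was deliberate, the SAP should record it.

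Three stronger readings are tempting, and the documents do not support them:
- *Safety data from treated children are being discarded.* No document shows a Group 2 patient enrolled or dosed, so this can only be said conditionally.
- *Group 2 has no planned analysis at all.* The protocol itself plans descriptive Group 2 summaries, and the SAP does not say it cancels them. The gap concerns the FAS- and SAF-based analyses in the SAP.
- *The study's main conclusion is compromised.* Protocol 2.1 restricts the primary objective to Group 1. The Group 2 objectives are secondary, descriptive and untested.

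One caveat also stands. A part of the SAP at its start was not available, so statements about what the SAP omits apply to the remaining text. Nothing there points to a Group 2 plan in the missing part.

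**Conclusion.** The two documents disagree on scope, and this should be put right. Under the SAP text available, any Group 2 patient dosed in the extension is excluded from every FAS- and SAF-based analysis, contrary to protocol 9.1, to the Group 2 summaries in protocol 9 to 9.5, and to all eight Group 2 objectives. The exclusion rule itself does not depend on any assumed number.

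Its practical weight does depend on Group 2 enrolment after 10 May 2016, which is unknown. With no enrolment, this is a documentation gap closed by a short statement. With one or more patients dosed and no report elsewhere, a secondary safety objective goes unreported in a study whose main purpose is safety. The primary objective stands in both cases.

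**What to change.** **If any Group 2 patient was enrolled:**
- Add FAS-2 and SAF-2 to the SAP. Require at least one extension dose for FAS-2, as FAS-1 and SAF-2 already do. Copying protocol 9.1 unchanged would bring in a FAS-2 with no dosing condition.
- Add single-arm descriptive tables from Baseline 2: LS-BMD Z-score, BMC and bone markers at Months 6 and 12; pain at Months 3, 6, 9 and 12; bone age and metacarpal cortical width at Month 12; new clinical and morphometric vertebral fractures over the 12 months.
- Add adverse event, laboratory and vital-sign tables on SAF-2.
- Reconcile the visit labels. Protocol 9.5.1.1 and 9.5.1.2 use Months 18 and 24 for Group 2, while the Group 2 objectives use Months 6 and 12.

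**If no Group 2 patient was enrolled, or Group 2 is reported elsewhere:** state this in the SAP as a change from the protocol. If nobody was enrolled, also declare the Group 2 objectives not assessed.

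**Cost:** a modest amount of descriptive programming in the first case, because most SAP tables are laid out by Core treatment group and need a single-arm version; a sentence or two in the second. Neither needs new data collection or any hypothesis test.
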